4.3.2 Main analytical approach

The primary analysis of the primary endpoint is to compare the responder rate of the BIVV009 treatment arm with the placebo treatment arm via the COVID-adjusted Composite estimand as defined in [Table 6](#) below.

To reject the null hypothesis of no treatment difference, the two-sided p-value based on a stratified Cochran-Mantel-Haenszel (CMH) test must be < 0.05 . The test will be stratified by baseline hemoglobin ($<$ median baseline Hgb vs \geq median baseline Hgb) and geographic region (Japan/Australia, United States, Europe). In the case of completely unbalanced strata (all records within any strata fall within a single treatment arm), the CMH test will be stratified only by baseline hemoglobin.

Table 6 - COVID-adjusted composite estimand for primary analysis

COVID-adjusted Composite Estimand	
Population	FAS
Response variable	Responder if

COVID-adjusted Composite Estimand	
	
 Free of post-baseline transfusion within the range of Week 5 and Week 26 visit dates, and The change from baseline in Hgb at treatment assessment timepoint ≥ 1.5 g/dL, and Receive no protocol prohibited medications defined in Section 4.1 within the range of Week 5 and Week 26 visit dates
ICEs handling	
 Subjects who early discontinue study prior to Week 23, for reasons other than COVID, are considered non-responders Subjects with no Hgb data from Week 23, 25, and 26, for reasons other than COVID, are considered as non-responders If a subject has a COVID-related infusion gap (defined as 2 consecutive missed infusions due to COVID-19), transfusions received and protocol-prohibited CAD medications taken during the infusion gap and within the 5 weeks following the infusion gap will not be included in the responder derivation.
Measure of treatment effect	
 Odds ratio of the proportion of responders in BIVV009 and Placebo using the Cochran-Mantel-Haenszel test Subjects missing infusions at Week 23 and 25 due to COVID will have their Hgb at TAT imputed using multiple imputation with an MMRM approach.

Multiple imputation (n=100 imputations) will first be run on subjects who missed both the Week 23 and 25 study visits due to COVID-19 to fill in their missing Hgb data at TAT. A CMH test will be conducted on each imputation and the chi-square statistics will be pooled using Rubin's Rules, together with the pooled CMH odds ratio and a 95% confidence interval for the odds ratio will be computed.

In addition, the proportion of subjects who meet each of the three response criteria will be summarized by treatment group. A separate table for the number of transfusions by study period (before Week 5 and between Week 5 and Week 26) and by treatment arm will be generated.

If there are no patients who missed both the Week 23 and 25 study visits due to COVID-19, the primary efficacy analysis would be completed using the Composite estimand ([Section 4.3.3.1](#)).

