**Table 2 - Responder definition**

A patient will be considered a responder in Part A if:

- Hgb increases  $\geq 1.5$  g/dL from baseline (defined as the last Hgb value before administration of the first dose of study drug) at treatment assessment endpoint (defined as mean value from Weeks 23, 25, and 26) and
- The patient did not receive a blood transfusion from Week 5 through Week 26 (EOT), and
- The patient did not receive treatment for CAgD beyond what is permitted per protocol from Week 5 through Week 26 (EOT)

A list of excluded concomitant medications, as well as allowed concomitant medications with restrictions, is provided in [Section 6.2.6](#). Beyond the permitted concomitant medications, study drug, and transfusions, patients may receive no other therapies for the treatment of CAgD while enrolled in this study; patients requiring other treatment for their CAgD in Part A will be withdrawn from the study and counted as non-responders. These patients will not be eligible to participate in Part B.

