## 5.2 EXCLUSION CRITERIA

Patients who meet any of the following criteria will be excluded from the study:

- E 01. Cold agglutinin syndrome secondary to infection, rheumatologic disease, or active hematologic malignancy.
- E 02. History of blood transfusion within 6 months of screening, or history of more than one blood transfusion within 12 months of screening.
- E 03. Clinically relevant infection of any kind within the month preceding enrollment (eg, active hepatitis C, pneumonia).

- E 04. Clinical diagnosis of SLE; or other autoimmune disorders with anti-nuclear antibodies at Screening. Anti-nuclear antibodies of long-standing duration without associated clinical symptoms will be adjudicated on a case-by-case basis during the Confirmatory Review of Patient Eligibility ([Section 6.1.1.3](#)).
- E 05. Positive hepatitis panel (including hepatitis B surface antigen and/or hepatitis C virus antibody) prior to or at Screening.
- E 06. Positive human immunodeficiency virus (HIV) antibody at Screening.
- E 07. Treatment with rituximab monotherapy within 3 months or rituximab combination therapies (eg, with bendamustine, fludarabine, ibrutinib, or cytotoxic drugs) within 6 months prior to enrollment.
- E 08. Concurrent treatment with corticosteroids other than a stable daily dose equivalent to  $\leq 10$  mg/day prednisone for previous 3 months.
- E 09. Erythropoietin deficiency. Concurrent treatment with erythropoietin is permitted if the patient has been on a stable dose for the previous 3 months.
- E 10. Concurrent usage of iron supplementation unless the patient has been on a stable dose for at least 4 weeks.
- E 11. Clinically significant medical history or ongoing chronic illness that would jeopardize the safety of the patient or compromise the quality of the data derived from his/her participation in this study (as determined by the Investigator [or designee]) at Screening.
- E 12. Concurrent treatment with other experimental drugs or participation in another clinical trial with any investigational drug within 30 days or 5 half-lives, whichever is greater, prior to treatment start.
- E 13. Females who are pregnant, lactating, or, if having reproductive potential, are considered potentially unreliable with respect to contraceptive practice.
- E 14. History of hypersensitivity to BIVV009 or any of its components.

For home infusion in/exclusion criteria see ([Appendix K](#)).

For undiluted infusion eligibility criteria see [Section 4.1](#).

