these visits, it will be calculated as the average of the available values, unless no value is available from all three visits.

COVID-related infusion gap

COVID-related infusion gap is defined as 2 or more consecutive missed scheduled infusions due to COVID-19. For the primary endpoint analysis, transfusions and protocol-prohibited CAD medications received during a COVID-related infusion gap and within the first 5 weeks of infusion resumption will not preclude a subject from being a responder.

Solicited Symptomatic Anemia

The severity of CAD symptomatic anemia is defined in [Table 5](#). The severity grading for symptomatic anemia is adopted based on Common Toxicity Criteria for Adverse Events (CTCAE) grades and is collected in eCRFs at every visit.

Table 5 - Severity grade for symptomatic anemia related CAD

CAGD Symptomatic Anemia Term	Grade 1	Grade 2	Grade 3	Grade 4
Fatigue	Fatigue relieved by rest	Fatigue not relieved by rest; limiting instrumental ADL	Fatigue not relieved by rest; limiting self care ADL	Not defined
Weakness	Uneasiness or lack of well being	Uneasiness or lack of well being; limiting instrumental ADL	Not defined	Not defined
Shortness of Breath	Shortness of breath with moderate exertion	Shortness of breath with minimal exertion; limiting instrumental ADL	Shortness of breath at rest; limiting self care ADL	Life-threatening consequences; urgent intervention indicated
Palpitations, fast heart beat	Mild symptoms; intervention not indicated	Intervention indicated	Not defined	Not defined
Lightheadedness	Not defined	Present (eg, near fainting)	Not defined	Not defined
Chest Pain	Mild pain	Moderate pain; limiting instrumental ADL	Pain at rest; limiting self care ADL	Not defined

ADL = activities of daily living

Thromboembolic Events

The thromboembolic events prior to study entry are recorded as medical history in the eCRFs, notably pre-specified categories of TE events occurring within 1 year prior to screening are captured, while thromboembolic events on study are captured as adverse events. Both medical history and adverse events will be coded according to Medical Dictionary for Regulatory Activities (MedDRA) v20.1 (or higher).

In general, thromboembolic events may include but are not limited to:

- Any venous events
 - Portal vein obstruction
 - Deep vein thrombosis
 - Pulmonary embolism
 - Mesenteric (abdominal) venous thrombosis
- Any cerebral events

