4.3 PRIMARY ENDPOINT(S) ANALYSIS

4.3.1 Definition of endpoint(s)

The primary endpoint is the responder rate, defined in [Section 1.2](#), and is a composite endpoint of the following components:

1. Free of post-baseline transfusion within the range of Week 5 and Week 26 visit dates;
2. Change from baseline in Hgb at treatment assessment timepoint is ≥ 1.5 g/dL,
3. Receive no protocol prohibited medications (defined in [Section 4.1](#)) within the range of Week 5 and Week 26 visit dates

Components 1 and 3 will be determined by the corresponding questions in eCRF at all visits (from Week 5 through Week 26) in Part A.

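### When the COVID-adjusted estimand is primary, waived transfusions and prohibited CAD drugs are ignored but the Hgb values that follow them are still scored

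*SAP*

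**What the plan says.** Part A SAP 4.3.2 makes the COVID-adjusted composite estimand (Table 6) the primary analysis. Three rules matter here.

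- **Waiver.** "COVID-related infusion gap is defined as 2 or more consecutive missed scheduled infusions due to COVID-19" (SAP 4.1). For a patient with such a gap, "transfusions received and protocol-prohibited CAD medications taken during the infusion gap and within the 5 weeks following the infusion gap will not be included" when response is derived (Table 6). SAP 4.1 says that transfusions and prohibited CAD drugs "received during a COVID-related infusion gap and within the first 5 weeks of infusion resumption will not preclude a subject from being a responder".
- **Hgb component.** "Change from baseline in Hgb at treatment assessment timepoint is ≥ 1.5 g/dL" (SAP 4.3.1). Under SAP 4.1 this value is the mean of whichever Week 23, 25 and 26 results are available. Nothing excludes results obtained after rescue.
- **Imputation.** "Subjects missing infusions at Week 23 and 25 due to COVID will have their Hgb at TAT imputed" (Table 6). This is the only replacement rule for Hgb in the primary analysis.

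The last paragraph of SAP 4.3.2 sets a condition: if nobody missed both the Week 23 and Week 25 visits because of COVID-19, the Composite estimand, which has no waiver, becomes primary.

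Two other passages point the other way. For the key secondary Hgb endpoint, the hypothetical estimand in SAP Table 9 sets every value after transfusion or prohibited medication to missing. Protocol 4.1, after Table 2, states that "patients requiring other treatment for their CAgD in Part A will be withdrawn from the study and counted as non-responders". Protocol Section 7 gives the SAP precedence where the two differ.

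**The concern.** The primary objective is a Hgb rise together with avoidance of transfusion. The transfusion and medication components exist so that a rise produced by rescue is not credited to study drug. The waiver switches those components off around a gap but leaves the Hgb component untouched, so a rise caused by rescue can satisfy it.

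Take a patient who misses the Week 19 and 21 infusions, is transfused at Week 22 and resumes at Week 23. The transfusion is ignored, imputation is not triggered, and the Week 23, 25 and 26 values, all taken after the transfusion, decide responder status.

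The primary endpoint therefore has weaker protection against rescue than the secondary Hgb endpoint has in the same SAP. At stake is misclassification of single patients in a trial of about 40.

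**Working it through.** **Inputs.** Infusions at Weeks 0, 1, 3, 5 … 23, 25 (Protocol 4.1); gap of two consecutive missed infusions (SAP 4.1; longer gaps also qualify but are not listed here); scored visits Weeks 23, 25 and 26 and threshold 1.5 g/dL (SAP 4.1, 4.3.1); 20 per arm and 87% power at 85% v 35% (Protocol 7.10).

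**The plan's own figure.** Exact enumeration of a two-sided Fisher test, 20 v 20 at 85% and 35%, gives 87.5%, so the stated 87% reproduces. It is used below only for scale.

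**Step 1: which gaps leave the waiver open at a scored visit.** With Weeks w and w+2 missed, dosing resumes at w+4. Counted from resumption (SAP 4.1), the waiver ends at w+4+5 = w+9. Counted from the last missed dose (one reading of Table 6), it ends at w+2+5 = w+7.

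| Missed weeks | Ends (from resumption) | Scored visits inside | Ends (from last missed dose) | Scored visits inside | Hgb used |
|---|---|---|---|---|---|
| 13+15 | 22 | none | 20 | none | observed |
| 15+17 | 24 | 23 | 22 | none | observed |
| 17+19 | 26 | 23, 25, 26 | 24 | 23 | observed |
| 19+21 | 28 | 23, 25, 26 | 26 | 23, 25, 26 | observed |
| 21+23 | 30 | 25, 26 (23 missed) | 28 | 25, 26 | observed |
| 23+25 | n/a | n/a | n/a | n/a | imputed |

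A waived transfusion before Week 23 may also raise later scored values. How long the effect lasts is not in the documents.

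**Step 2: the rise needed.** Let d be the change from baseline without transfusion (negative if Hgb had fallen), m the number of available values and k the number raised by r. The mean change is d + r·k/m, so response requires r ≥ (1.5 − d)·m/k.

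- d = 0: 1.5 g/dL if all available values are raised, 2.25 if 2 of 3, 4.5 if 1 of 3.
- d = +0.5: 1.0, 1.5 and 3.0.
- d = −0.6 (for example baseline 9.5, pre-transfusion 8.9): 2.1, 3.15 and 6.3.

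Negative d is realistic. Entry allows Hgb up to 10.0 g/dL, while transfusion requires Hgb below 9 with symptoms or below 7 without.

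**Step 3: illustration on assumed figures.** The documents give no rise per unit. Assume 1 g/dL per unit, declining by 0.05 to 0.15 g/dL per unit per week, with two units at Week 22 (1, 3 and 4 weeks before the scored visits).

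- Slow decline: (1.9 + 1.7 + 1.6)/3 = 1.73 g/dL.
- Fast decline: (1.7 + 1.1 + 0.8)/3 = 1.20 g/dL.
- One unit gives half: 0.60 to 0.87 g/dL.

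These are rises from the pre-transfusion level. With d = 0, two units reach 1.5 only if total decline L satisfies 2 − L·(1+3+4)/3 ≥ 1.5, so L ≤ 0.19 g/dL per week (about 0.09 per unit). With d = −0.6 the net change is 0.60 to 1.13, a non-response. One unit alone does not suffice at d = 0.

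**Step 4: scale.** One patient is 1/20 = 5 percentage points. On an unstratified Mantel-Haenszel test, 14/20 v 7/20 gives p = 0.029 and 13/20 v 7/20 gives p = 0.061. If 1, 2 or 3 responders (assumed counts) in the BIVV009 arm were created by rescue, removing them takes 85% to 80, 75 or 70%, and Fisher power against 35% from 87.5% to 75.7, 61.4 or 46.8%. In the placebo arm, removal takes 35% to 30, 25 or 20% and power rises to 93.1, 96.6 or 98.7%.

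**The case against.** The strongest reply is that this is a narrow path, already covered by other analyses. The waiver operates only if some patient missed both Week 23 and Week 25, and the affected patient must be a different one, with an earlier gap, a transfusion in the window and a sufficient rise. Protocol 2.2 describes transfused cells as exposed to the same destruction and of limited benefit beyond short-term relief. The waiver applies to both arms. Sensitivity I drops it in the same population, Sensitivity II removes patients with COVID-missed visits, and the per-protocol set removes everyone who missed two consecutive doses. Transfusions by period and arm are also tabulated.

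Much of this stands, and it lowers the severity. It does not close the gap. Once one patient triggers the COVID-adjusted estimand, the waiver covers every gap patient. Scored visits can fall within a week of transfusion. Applying a rule to both arms does not make its errors cancel. The sensitivity analyses would reveal a problem but would not change the primary p-value.

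The drug route is weaker than the transfusion route. Protocol 4.1 requires withdrawal of patients needing other CAgD treatment, and Table 6 counts non-COVID discontinuation before Week 23 as non-response, so few such patients should reach a scored value. A reader might cite exclusion E 07 ("Treatment with rituximab monotherapy within 3 months or rituximab combination therapies" with 3- and 6-month limits) as proof of carry-over beyond 5 weeks. It is an entry washout and says nothing about how long Hgb stays raised. What remains is a conflict between the SAP waiver and Protocol 4.1.

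**Conclusion.** The concern holds in a conditional form. When the COVID-adjusted estimand is primary, the rules as written can score Hgb raised by a waived transfusion as response. Three or four two-dose gap patterns leave the waiver open at a visit scored on observed Hgb, depending on where the 5 weeks start. That result uses only the schedule and the SAP's rules.

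Three stronger readings are tempting and are not supported:

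- that rescue routinely makes a responder: transfusion alone suffices only if it lifts the mean of the available Week 23, 25 and 26 values to at least 1.5 g/dL above baseline, which is harder if Hgb had first fallen below baseline;
- that the comparison is biased towards BIVV009: false responders can arise in either arm and the net direction is unknown;
- that the primary result is affected whatever happens: without a patient missing both late visits, the waiver is not used.

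The number of gap patients is not given, so the total effect cannot be sized beyond 5 percentage points per patient in an arm of 20. The g/dL figures in Step 3 are assumptions. This should be corrected before unblinding, but it ranks below a must-fix because it is conditional and the planned sensitivity analyses would show it.

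**What to change.** 1. Keep the waiver for the transfusion component. In the primary analysis, treat Hgb values after a waived transfusion or prohibited CAD medication as missing, using the Table 9 rule for the key secondary Hgb endpoint. A fixed cut-off such as 5 weeks is weaker: on the Step 3 assumptions two units would still contribute 2 − 5 × 0.3 = 0.5 to 2 − 5 × 0.1 = 1.5 g/dL at that point.
2. If no unaffected Week 23, 25 or 26 value remains, impute Hgb at the treatment assessment timepoint with the planned multiple imputation, and exclude post-rescue values from the imputation model. State that these patients do not fall under the rule making absent Hgb a non-response.
3. Reconcile the drug waiver (SAP Tables 3 and 6, Section 4.1) with the non-responder statement in Protocol 4.1.
4. Reconcile the start of the 5 weeks (SAP 4.1 v Table 6), the gap definition (two or more missed infusions in SAP 4.1, two in Table 6) and the imputation trigger (missed infusions in Table 6, missed visits in the text below it).

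The cost is SAP wording and minor programming before unblinding, with no change to sample size or alpha. The downside is slightly more imputed data and possibly a few fewer responders.

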### 7.3.2 Methods of analysis

Each patient in the FAS will be classified as a responder or non-responder per the response criteria, and will be compared between treatment groups using Cochran-Mantel-Haenszel test at the significance level of 0.05. The difference in the proportion of responders between groups will be calculated with a 95% exact confidence interval (CI). To assess the hematology component of response, the mean of the non-missing Hgb assessments at the Week 23, Week 25, and Week 26 analysis visits (treatment assessment endpoint) will be used. Visit windows will be used to assign analysis visits, as detailed in the SAP. Patients missing all three analysis visits will be counted as non-responders. Sensitivity analyses will be performed to evaluate the impact by the missing data, when appropriate. Details will be specified in the SAP.

Secondary endpoints, defined as follows, will be tested only when the primary endpoint is statistically significant:

1. Mean change from baseline in Hgb at the treatment assessment endpoint (mean of values at Week 23, 25, and 26)
2. Mean change from baseline in bilirubin (excluding patients with Gilbert's Syndrome) at the treatment assessment endpoint
3. Mean change from baseline in QOL, as assessed by the change in FACIT-fatigue scale scores at the treatment assessment endpoint
4. Mean change from baseline in LDH at the treatment assessment endpoint
5. Incidence of solicited symptomatic anemia at EOT

The change from baseline variables will be analyzed using analysis of covariance (ANCOVA) with baseline as covariate. A multiple testing procedure will be specified in the SAP to control the overall Type I error rate among the secondary endpoints.

As a sensitivity analysis, the efficacy analysis will be repeated with patients stratified by previous rituximab therapy and/or cytotoxic therapy versus patients who are naïve to rituximab therapy and/or cytotoxic therapy using the FAS.

Other efficacy assessments will be summarized by overall population using descriptive statistics, proportions and graphically where applicable.

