## 7.10 SAMPLE SIZE CONSIDERATIONS

Approximately 40 patients with primary CAgD who do not have a recent history of transfusion will be randomized.

With 40 patients (20 per group), there is 87% power to detect a statistically significant difference of 50% between the BIVV009 group and placebo group if the true response rates are 85% and 35% for the BIVV009 and placebo groups, respectively. This calculation assumes a 2-sided 5%-level test comparing the response rates between the BIVV009 and placebo groups. A 50% improvement over placebo is considered clinically relevant.

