2 SAMPLE SIZE DETERMINATION

Approximately 40 patients with primary CAD who do not have a recent history of transfusion will be randomized. There are limited data from the published literature or available natural history data to estimate the placebo response for the transfusion-independent study population. Since patients with evidence of ongoing hemolysis, hemoglobin <10 g/dL, and symptomatic are included in the study, it is expected that few patients would meet the responder definition for the primary endpoint without treatment intervention. The proposed sample size was chosen to provide sufficient power to detect a 50% improvement for BIVV009 over a range of possible placebo responder rates with a significance level of 0.05. A total of 40 patients (20 patients per group) provides a statistical power of greater than 85% to detect a treatment difference of 50% for placebo response rates between the range of 15% to 40%. This calculation assumes a 2-sided 5%-level test comparing the response rates between the BIVV009 and placebo groups. A 50% improvement over placebo is considered clinically relevant.

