4.3.4 Subgroup analyses

Definitions of subgroups

The following subgroups will be considered for the selected analyses:

- Age (<65 , ≥ 65)
- Gender (Female, Male)
- Baseline weight (<75 kg, ≥ 75 kg)

- Baseline Hgb level (<median, >= median g/dL)
- Previous rituximab monotherapy use (Yes, No)
- Previous rituximab monotherapy or rituximab and other cytotoxic therapy use (Yes, No)
- Prior thromboembolic events within the last 1 year (Yes, No)
- Previous reculizumab use (Yes, No)

In case of very few subjects (eg, <5) in a category, the cutoff value may be changed to suit the distribution of these factors.

Analysis Methods

The CMH odds ratio and 95% CI will be summarized for the subgroups defined above. As with the primary endpoint, the odds ratios for each subgroup will be stratified by baseline hemoglobin (< median baseline Hgb vs \geq median baseline Hgb) and geographic region (Japan/Australia, United States, Europe). The CMH test may not be stratified in the case of completely unbalanced strata. The consistency of the odds ratio among these sub-populations will be examined by forest plots.

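### The Part A SAP leaves out the protocol's responder-rate difference with exact CI and relies on a stratified odds ratio that is infinite in about 5–11% of trials at the design rates

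*SAP*

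**What the plan says.** Protocol 7.3.2 names the CMH test for the primary endpoint and then commits to an effect estimate: "The difference in the proportion of responders between groups will be calculated with a 95% exact confidence interval (CI"). Protocol 7.10 sizes the trial on the same scale: "With 40 patients (20 per group), there is 87% power to detect a statistically significant difference of 50" percentage points, "if the true response rates are 85% and 35% for the BIVV009 and placebo groups, respectively". Part A SAP section 2 repeats the 50-point target and adds: "A 50% improvement over placebo is considered clinically relevant".

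Part A SAP 4.3.2 stratifies the CMH test by median baseline Hgb and three regions, so up to six strata. If any stratum lies wholly in one arm, it falls back to Hgb alone. The effect measure is the odds ratio: "together with the pooled CMH odds ratio and a 95% confidence interval for the odds ratio will be computed". SAP Tables 3 and 6–8 and the four sensitivity analyses in 4.3.3 use the same measure. In 4.3.4, "the odds ratios for each subgroup will be stratified by baseline hemoglobin" and region, with leave not to stratify when strata are completely unbalanced.

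No responder-rate difference, and no CI for one, appears in the Part A SAP. Its version table records only the move from Fisher's exact test to CMH, and its Appendix 2 lists no change. Protocol section 7 gives the SAP precedence. Protocol version 8 (04 November 2020) is later than SAP version 2 (02 October 2020). It adopts the CMH test and still keeps the difference with exact CI.

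**The concern.** The two documents disagree on how the primary effect is to be estimated, and the one that governs omits the scale on which the trial was designed. An odds ratio cannot be set against a 50-point criterion unless the two rates are also known.

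The odds ratio is also fragile here. With 20 patients per arm, up to six strata and few non-responders expected on drug, the Mantel-Haenszel denominator can be zero. The SAP's fallback deals with strata that lie wholly in one arm, not with zero response cells, and the SAP names no continuity correction or exact odds ratio. The estimate can fail when the drug works best, for example with 20 of 20 responders. The trial could then reject its null hypothesis and have no usable effect size or interval.

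**Working it through.** **1. Inputs.** 40 patients, 1:1 (Protocol 7.10). Response rates 85% v 35% (Protocol 7.10). SAP section 2 claims power "greater than 85% to detect a treatment difference of 50% for placebo response rates between the range of 15% to 40" percent, which spans 65% v 15% to 90% v 40%. Blocks of 4 with no stratification factor named (SAP 1.1). Strata and fallback from SAP 4.3.2. The documents give no regional mix, so four were assumed (Japan-Australia/US/Europe): equal thirds, 20/20/60, 25/15/60 and 10/20/70.

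**2. The plan's own figure.** Exact enumeration over two Binomial(20) arms gives 87.5% power for a two-sided 5% Fisher test at 85% v 35%, matching the stated 87%. The chi-square/CMH version gives 92.8%.

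**3. What the odds ratio says about 50 points.** Odds ratio = [p1/(1−p1)] / [p0/(1−p0)].
- 85/35 and 65/15: (0.85×0.65)/(0.15×0.35) = (0.65×0.85)/(0.35×0.15) = 10.5
- 75/25: (0.75×0.75)/(0.25×0.25) = 9.0
- 90/40: (0.90×0.60)/(0.10×0.40) = 13.5

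The same 50-point difference therefore corresponds to odds ratios from 9.0 to 13.5.

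**4. When it fails.** The Mantel-Haenszel odds ratio is Σ(a·d/n) / Σ(b·c/n), where b is non-responders on BIVV009 and c is responders on placebo in each stratum. It is infinite, and the usual log-scale CI cannot be computed, when b·c = 0 in every stratum. Without strata the probability is 1 − (1 − p1^n1)(1 − (1−p0)^n0). At 85/35 with 20 per arm: 0.85^20 = 0.0388 and 0.65^20 = 0.0002, giving 3.9%. At 90/40 it is 12.2%.

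**5. Whole trial under the SAP rule.** 20,000 simulated trials per scenario, fallback applied, strata not prognostic; ranges are over the four mixes:

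| Rates | Odds ratio infinite |
|---|---|
| 85/35 | 5.4–10.5% |
| 75/25 | 2.1–6.4% |
| 65/15 | 5.8–10.6% |
| 90/40 | 13.6–19.9% |

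Swapping arms and outcomes turns 85/35 into 65/15, so those two rows estimate the same quantity: about 5–11%. If baseline Hgb shifts response by ±10 points at 85/35, the figure is 10.7–16.1% (equal and 20/20/60 mixes).

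**6. Subgroups at 85/35.** SAP 4.3.4 does not say whether its fallback drops all strata or only region, so both readings were run:

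| Patients in subgroup | Drop all strata | Keep Hgb strata |
|---|---|---|
| 20 | about 22% | about 29% |
| 14 | about 37% | about 48% |
| 10 | about 51% | about 64% |

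The closed form in step 4, with equal arms, gives 20.8%, 35.4% and 50.8%, in line with the first column. At 12 patients the figures are 42% (unstratified closed form) and 56%, so both readings exceed one half only at about 10 or fewer.

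**7. Imputation.** If COVID-related imputation is triggered, 100 data sets are analysed. One infinite estimate among them prevents pooling of the log odds ratio by Rubin's rules.

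**8. The difference in the same situations.** Exact unconditional 95% CI from the inverted score statistic:
- 17/20 v 7/20: 85 − 35 = 50 points (about 18 to 74)
- 20/20 v 7/20, where the odds ratio is infinite: 100 − 35 = 65 points (about 41 to 85)

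**The case against.** The SAP is not silent on rates. It tabulates the proportion meeting each of the three response components by arm (4.3.2) and counts Hgb rises of at least 1.5 g/dL by arm (4.4.2). A reader could probably work out a crude difference. That stands in part; what is missing is the between-arm difference in the composite responder rate and its CI.

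The size depends on the scenario. At 75/25 it is only 2–6%, the top of the range needs 90/40, and 3.9% at 85/35 arises with no stratification at all. These limits stand. The pooling problem also arises only if someone missed both the Week 23 and Week 25 visits because of COVID-19; otherwise SAP 4.3.2 uses the Composite estimand and nothing is pooled.

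Four stronger readings are tempting, and the documents do not support them:
- *The primary test fails.* It does not. The CMH p-value stays defined when the odds ratio is infinite.
- *The forest plot would be mostly non-estimable.* That needs six strata kept in every subgroup, which gives roughly 47% at 20 patients and 80% at 10. SAP 4.3.4 allows stratification to be dropped and cutoffs to be changed. Some factors also split near half: Hgb at its median, and weight at 75 kg against an expected median of 74.8 kg (Protocol 2.2.3).
- *Stratifying the Hgb subgroups by Hgb is an error.* With the trial-wide median, each such subgroup has one Hgb level and the factor drops out.
- *The odds ratio should give way to the difference as main measure.* The odds ratio pairs naturally with the CMH test, which was adopted on FDA feedback. Ranking one above the other is a preference.

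**Conclusion.** The point holds in a limited form. The protocol's responder-rate difference with exact CI is missing from the governing SAP without a recorded reason, although both documents define clinical relevance on that scale. The odds ratio that remains is infinite, with no usable CI, in about 5–11% of trials at 85/35, 2–6% at 75/25, 5–11% at 65/15 and 14–20% at 90/40. In subgroups this happens in about 22–29% at 20 patients, 37–48% at 14 and 51–64% at 10.

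The omission is a matter of text and rests on no assumption. The percentages rest on assumed regional mixes, non-prognostic strata and, for subgroups, the 85/35 rates. A prognostic baseline Hgb would raise the whole-trial figures. Type I error and the decision on the primary hypothesis are not affected. What is at risk is the effect estimate that should accompany that decision.

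**What to change.** - **SAP 4.3.2 and 4.3.3:** beside the CMH test and odds ratio, report the responder-rate difference with the protocol's exact 95% CI, unstratified.
- **If multiple imputation is used:** pool a Mantel-Haenszel stratified difference and its 95% CI by Rubin's rules. Give the exact CI for the Composite estimand, which needs no imputation.
- **SAP 4.3.4:** add unstratified rate differences with exact CIs for each subgroup to the forest plot.

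The cost is SAP wording and a few extra output lines. The test, its stratification and alpha stay as they are.
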